Efficacy Evaluation		
The same blinded evaluator will perform Investigator Global Assessments and lesion counting at Screening, Baseline, and Weeks 2, 4, 8, and 12. In the event that this is not possible due to unforeseen circumstances, a different blinded evaluator will evaluate the subject. However, the same evaluator should evaluate subjects at the Baseline and Week 12 evaluations.
 
Investigator Global Assessment (IGA) The IGA score will be determined based on the Investigator evaluation of the overall signs and symptoms of acne vulgaris. IGA evaluations will be performed prior to the lesion counts, approximately 3 feet from the subject, and scored on a scale of 0 (clear) to 4 (severe).
 
Lesion Counts At Screening, Baseline, and Weeks 2, 4, 8, and 12, the Investigator will count the total number of non-inflammatory and inflammatory lesions on the subject's face including the forehead, right and left cheeks, chin and nose. Non-inflammatory lesion count will include the number of open and closed comedones, which will be recorded separately.
		

Name of Sponsor/Company: Novan, Inc.	Individual Study Table Referring to Part of the Dossier:	(For National Authority Use Only)
Name of Finished Product: SB204	Volume:	
Name of Active Ingredient: NVN1000	Page:	
Inflammatory lesion count will include the number of papules and pustules, which will be recorded separately. The number of nodules and cysts will be reported separately and included with the inflammatory lesion counts.		
Tolerability Evaluation	Subjects will be assessed at each visit from Baseline through Week 12 for cutaneous tolerability. Tolerability will be assessed on a scale of 0 to 3 where 0=none, 1=mild, 2=moderate, and 3=severe for erythema, scaling, dryness, pruritus, and burning/stinging.	

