3.1 STUDY ENDPOINTS

3.1.1 EFFICACY ENDPOINTS

Primary Efficacy Endpoints

The co-primary efficacy endpoints are:

- The absolute change in inflammatory lesion count from Baseline to Week 12;
- The absolute change in non-inflammatory lesion count from Baseline to Week 12;
- The proportion of success according to the dichotomized IGA. A subject will be considered a success if the IGA at Week 12 is clear or almost clear and is at least 2 grades less than Baseline.

Secondary Efficacy Endpoints

The secondary efficacy endpoints include the following:

- The percent change in inflammatory lesion count from Baseline to Week 12;
- The percent change in non-inflammatory lesion count from Baseline to Week 12;
- The median time to improvement.

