3.7.2 INCLUSION CRITERIA

Each subject must fulfill all of the following inclusion criteria to participate in the study:

1. Have a signed written informed consent form (ICF). Subjects less than 18 years of age or the age of majority in their state must sign an assent form for the study and a parent or a legal guardian must sign the informed consent;
2. Be male or female, 12 to 40 years of age, inclusive and in good general health;
3. Have a baseline IGA score of moderate (3) or severe (4);
4. Have a minimum of 25 but not more than 70 non-inflammatory lesions (open and closed comedones) on the face;
5. Have a minimum of 20 but no more than 40 inflammatory lesions (papules and pustules) on the face;
6. Have no more than two nodules or cysts on the face;
7. Women of childbearing potential (WOCBP) must have a negative urine pregnancy test (UPT) prior to randomization;
8. WOCBP must agree to use an effective method of birth control during the course of the study and for 30 days after their final study visit; females taking hormonal contraceptives must have taken the same type for at least three months (90 days) prior to entering the study and must not change type during the study. Those who have used hormonal contraceptives in the past and stopped must have discontinued usage at least three months prior to the start of the study;
9. Males must agree to avoid fathering a child during the study and for 60 days after the last dose of the study drug by ensuring one of the acceptable methods of contraception listed is used and not donating sperm; and
10. Be willing and able to follow study instructions and likely to complete all study requirements. Subjects under 18 years of age or age of majority must be accompanied by the parent or legal guardian at the time of assent/consent signing.

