7.5.1 SENSITIVITY EFFICACY ANALYSES

A sensitivity analysis will use the method of Markov Chain Monte Carlo (MCMC) multiple imputation to impute missing data for the non-inflammatory and inflammatory lesion counts and IGA at Week 12. This method does not rely on the assumption of data missing at random. Additionally, the pattern of missing observations in each treatment group cannot influence the missing value estimation in the other because the imputation is being conducted independently for each treatment group.

Lesion Counts

Multiple imputation and subsequent analysis will involve four distinct phases with these principal tasks:

1. Calculate the number of missing values to be estimated by MCMC (nmiss) for 12 week value.
2. Create a data set of subjects, one for each treatment group, with observed values and those needing estimation by MCMC. The missing lesion count values in each data set will be filled in using the MCMC method ‘5 x nmiss’ times to generate ‘5 x nmiss’ data sets. The resulting data sets for each treatment group will be combined into one complete data set for each imputation.

Syntax:

```
proc mi data=datain out=dataout seed=&seed. nimpute=5xnmiss;
  where trtpn=(1, 2,, 3, 4, or 5);
  mcmc chain=multiple;
  var lescnt2-lescnt5;
run;
```

3. For each complete data set, the absolute change in non-inflammatory lesion counts and absolute change in inflammatory lesion counts for baseline minus the 12 week value will be computed. Each complete data set will be analyzed as specified for the particular analysis.

The results from these analyses will be combined into a single inference using SAS PROC MIANALYZE.

IGA

The sensitivity analysis for the IGA multiple imputation will involve four principal tasks:

1. Calculate the number of missing values, by treatment group, for IGA (total from Weeks 2, 4, 8, and 12).
2. Missing values will be filled in '5 x nmiss' times to generate '5 x nmiss' complete data sets, where nmiss is the maximum number of missing values of both treatment groups. The resulting imputed datasets for each treatment group will be combined into one complete dataset by imputation number.

Syntax:

```
proc mi data=datain out=dataout seed=&seed. n impute=5 x nmiss;
  where trtpn=(1, 2, 3, 4, or 5);
  mcmc chain=multiple;
  var IGA1 IGA2 IGA4 IGA8 IGA12;
run;
```

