3. For each complete dataset, dichotomous endpoints (defined as IGA = 0 or 1 and at least a two-grade reduction from Baseline) will be computed. The imputed IGA values will be rounded to the nearest integer value prior to computing the dichotomized endpoints. Each complete data set will be analyzed with a Cochran-Mantel-Haenszel test.

Results from these analyses will be combined into a single inference using SAS® PROC MIANALYZE.

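### In the IGA imputation sensitivity analysis, an imputed score that rounds below 0 is counted as a failure, because success is defined as exactly 0 or 1 and nothing keeps imputed values on the 0–4 scale

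*Protocol*

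**What the plan says.** Section 3.1.1 defines the co-primary IGA endpoint in words: a subject is a "success if the IGA at Week 12 is clear or almost clear and is at least 2 grades less than Baseline". The scale has five grades, 0 to 4 (Section 4.2.1 and Appendix 3), and Section 3.7.2 requires a Baseline score of 3 or 4.

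Section 7.1 handles missing Week 12 values mainly by LOCF and adds multiple imputation as a sensitivity analysis. Section 7.5.1 fixes three parts of that analysis for the IGA:

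- **The model.** The printed PROC MI call uses "mcmc chain=multiple" with "var IGA1 IGA2 IGA4 IGA8 IGA12". This is imputation under a multivariate normal model with the IGA treated as continuous. The call contains no MINIMUM=, MAXIMUM= or ROUND= option. It is run by arm: "the imputation is being conducted independently for each treatment group".
- **The rounding.** "The imputed IGA values will be rounded to the nearest integer value prior to computing the dichotomized endpoints".
- **The scoring.** In each completed data set, "dichotomous endpoints (defined as IGA = 0 or 1 and at least a two-grade reduction from Baseline) will be computed".

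No part of the protocol limits imputed values to the 0–4 scale or says how a rounded value below 0 is scored.

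**The concern.** On observed data, a score of 0 or 1 and a score of at most 1 are the same condition, because no observed score lies below 0. On imputed data they differ. A normal draw has no floor, so some draws fall below -0.5 and round to -1 or lower. The printed rule scores those as failures, while a draw of 1.4, which rounds to almost clear, is a success. A better imputed outcome is thus scored worse than a poorer one.

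Draws off the top of the scale do no such harm, since a value above 4 is a failure under either rule. The error therefore only removes successes.

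At stake is the only missing-data sensitivity analysis that the protocol states for the IGA endpoint. Two programmers given the same imputed data, one coding the printed rule and one coding the endpoint as worded, would report different results.

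**Working it through.** **No plan figure to reproduce.** The protocol gives no expected IGA mean, SD, response rate or dropout rate. The only related arithmetic is the allocation in Section 7.8: 200 × 2/8 = 50 per active arm and 200 × 1/8 = 25 per vehicle arm, which agrees with the stated sizes.

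**Step 1: the rule applied to one value.** Take Baseline 3 and an imputed Week 12 value of -0.6.
- It rounds to -1.
- The reduction is 3 - (-1) = 4 grades, so the two-grade condition is met.
- It is neither 0 nor 1, so it is scored a failure. Under a rule of 1 or less it is a success.

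**Step 2: how often this can happen.** For a normal draw with mean m and SD s, the chance of rounding to -1 or lower is Φ((-0.5 - m)/s). The chance of rounding to 1 or lower is Φ((1.5 - m)/s). Their ratio is the share of imputed successes lost. Means and SDs are assumed.

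| Mean | SD | P(below -0.5) | P(below 1.5) | Share lost |
|---|---|---|---|---|
| 2.0 | 0.8 | 0.09% | 26.6% | 0.3% |
| 2.0 | 1.0 | 0.62% | 30.9% | 2.0% |
| 1.5 | 0.8 | 0.62% | 50.0% | 1.2% |
| 1.5 | 1.0 | 2.28% | 50.0% | 4.6% |
| 1.0 | 0.8 | 3.0% | 73.4% | 4.1% |
| 1.0 | 1.0 | 6.7% | 69.2% | 9.7% |

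The loss is concentrated in subjects who were doing well before they left. Assume mean 1.5 and SD 0.9 at Weeks 8 and 12, correlation 0.7, and imputation from Week 8 alone. A subject who is clear at Week 8 then has a Week 12 draw with mean 1.5 + 0.7 × (0 - 1.5) = 0.45 and SD 0.9 × √(1 - 0.49) = 0.64. The chance of falling below -0.5 is Φ(-0.95/0.64), about 7%.

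**Step 3: effect on an arm's success rate.** A simulation imputed each arm separately by multivariate-normal data augmentation. It assumed five visits, serial correlation 0.7 and 10% or 20% dropout, with 25 replicates of 20 imputations. Success was scored both ways.

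| Arm (assumed Week 12 mean) | n | Dropout | As printed | 1 or less | Loss (points) |
|---|---|---|---|---|---|
| Active (2.0) | 50 | 10% | 28.00% | 28.05% | 0.05 |
| Active (2.0) | 50 | 20% | 28.00% | 28.11% | 0.11 |
| Vehicle (2.4) | 25 | 10% | 12.21% | 12.26% | 0.05 |
| Vehicle (2.4) | 25 | 20% | 15.42% | 15.58% | 0.16 |
| Vehicle (2.2) | 25 | 10% | 21.66% | 21.74% | 0.08 |
| Vehicle (2.2) | 25 | 20% | 21.44% | 21.74% | 0.30 |
| Active (1.5) | 50 | 10% | 50.45% | 50.74% | 0.29 |
| Active (1.5) | 50 | 20% | 49.25% | 49.92% | 0.67 |
| Active (1.2) | 50 | 10% | 62.30% | 62.78% | 0.48 |
| Active (1.2) | 50 | 20% | 61.58% | 62.41% | 0.83 |

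Between about 0.5% and 5% of imputed values rounded below 0.

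**Step 4: effect on the contrast, at 20% dropout.**
- Modest effect (2.0 against 2.4): printed 28.00 - 15.42 = 12.58 points; corrected 28.11 - 15.58 = 12.53. The printed rule overstates the difference by 0.05.
- Large effect (1.5 against 2.2): printed 49.25 - 21.44 = 27.81; corrected 49.92 - 21.74 = 28.18. The printed rule understates it by 0.37.

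At 10% dropout the modest-effect contrast is 15.79 points under both rules.

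**Precision.** In the modest case few draws are affected. For the vehicle arm at 20% dropout, 25 × 25 × 0.20 × 20 = 2,500 imputed values at 0.66% is about 16 draws. The simulation supports saying that the losses are similar there. It does not support ranking the arms to a hundredth of a point.

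**The case against.** **The printed code is schematic.** The number of imputations is written as a product and the WHERE clause lists alternatives, so neither line would run. Rounding is required in the text but absent from the call, so some handling clearly takes place outside it. Missing bounds in the call are therefore weak evidence that out-of-range values go unhandled. This has force for the code. It does not reach the scoring sentence in step 3, which is plain text and gives the wrong answer for a value below 0.

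**This is detail for the SAP, and the intent is obvious.** Section 7.1 does defer detail to the SAP, and a sensible programmer would probably code a value of 1 or less. But the protocol did not leave the rule open: it printed one, and following it gives a result at odds with Section 3.1.1.

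**Nothing turns on it.** One subject in an active arm of 50 is 2 percentage points. The largest loss found, 0.83 points, is less than half a subject, in a sensitivity analysis of a Phase 2 trial that makes no multiplicity adjustment. The per-protocol analysis also gives a comparison based largely on subjects who attended Week 12. All of this stands, and it is why the point is minor.

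**A stronger reading to avoid.** A reader might infer that the lost successes fall mostly in the better arm, so that the analysis is biased against the more effective treatment. At equal SD and equal precision a lower mean does lose more: for means of 1.75 against 2.25 the ratio of the chances of falling below -0.5 is 4.1 at SD 1.0 and 8.4 at SD 0.8. But each vehicle arm is imputed separately with about 25 subjects, and the extra parameter uncertainty widens its tails. With a modest effect that offsets the difference in means. The number of missing values per arm also drives the loss, and it is unknown. A reader might likewise infer that good imputed outcomes in general are lost; imputed values of 0 and 1 still count as successes.

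**Conclusion.** The rule is wrong as written, and the consequence is minor. Section 7.5.1 combines an unbounded imputation, rounding to the nearest integer, and a success rule that excludes values below 0. An imputed score beyond clear is therefore counted as a failure.

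The sign is certain within an arm: the printed rule can only lower the imputed success rate. The size is not certain, because the Week 12 means, SDs, correlation and dropout were all assumed. Across those assumptions the loss ran from about 0.05 to 0.8 percentage points. The sign of the effect on the active-versus-vehicle contrast is not determined by the protocol: it was negligible or slightly in favour of active for a modest effect, and against active for a large one.

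Observed scores and the LOCF analysis are untouched.

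**What to change.** In Section 7.5.1, IGA step 3, replace the scoring rule with: after rounding, imputed IGA values below 0 are set to 0 and values above 4 are set to 4; success is a resulting IGA of 1 or less together with a drop of two or more grades from Baseline.

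Apply the limits after the draw rather than through MINIMUM= and MAXIMUM= in PROC MI, so that the imputation model stays as specified. If the SAP repeats the printed rule, make the same change there.

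The cost is one sentence and one line of code. It needs no new data and changes no observed score.

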7. STATISTICAL ANALYSIS

7.1 GENERAL CONSIDERATIONS

All statistical processing will be performed using SAS® version 9.3 unless otherwise stated. Statistical significance will be based on two-tailed tests of the null hypothesis resulting in p-values of ≤ 0.05 unless stated otherwise. Inferential testing will compare each active treatment group to the combined Vehicle treatment group. Comparisons will not be performed between active treatments. Efficacy analyses will be performed for the intent-to-treat (ITT) and per-protocol (PP) populations. Safety analyses will be performed using the safety population.

For the dichotomized IGA, subjects will be considered a success if their IGA score is clear or almost clear and at least two grades less than Baseline.

For those subjects for whom no Week 12 assessments are available, the last observation will be carried forward (LOCF) in order to provide a value for efficacy parameters that are missing, primarily due to missed visits. Additionally, a sensitivity analysis to estimate missing efficacy data will be based on estimation using the method of Markov Chain Monte Carlo (MCMC) independently for each treatment group. All hypotheses will be two-sided at an alpha level of 0.05.

A detailed description of the statistical methodology and data reporting for this study will be provided in the Statistical Analysis Plan (SAP). The SAP will be finalized before the database is locked and released to Novan. Any deviations from the SAP will be justified in the clinical study report.

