7.5 EFFICACY ANALYSIS

Lesion counts will be summarized at each evaluation from Baseline through Week 12. Absolute and percent change in lesion counts will be summarized at Weeks 2, 4, 8, and 12. IGA scores will be summarized from Baseline through Week 12. The dichotomized IGA scores will be summarized at Weeks 2, 4, 8, and 12.

Primary Efficacy Analysis

The analysis of the absolute change in non-inflammatory lesion counts at Week 12 will be conducted using an analysis of covariance with factor of treatment and baseline lesion count as the covariate.

The analysis of the absolute change in inflammatory lesion counts at Week 12 will use the same method as the analysis of the non-inflammatory lesions.

The analysis of the dichotomized IGA scores at Week 12 will be analyzed with a Cochran-Mantel-Haenszel test.

Pairwise comparisons of each active treatment group to the combined vehicle treatment group will be computed without concern for controlling for multiplicity.

Secondary Efficacy Analyses

The analyses of percent change in inflammatory and non-inflammatory lesion counts at Week 12 will use the same method as the analysis of the non-inflammatory lesions.

The time to improvement will be compared between each of the active treatment groups and the combined Vehicle treatment group using the Kaplan-Meier method. An observation will be censored if improvement is not achieved by Week 12 (inclusive). The log-rank test will be used to compare time to response between each active treatment group and the combined Vehicle treatment group.

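### Free improvement: stratify the Week 12 IGA success test by baseline IGA (3 v 4); the protocol states no stratum

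*Protocol*

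**What the plan says.** Section 3.1.1 lists Week 12 IGA success as one of three co-primary endpoints. Section 7.5 gives its analysis in one sentence: "The analysis of the dichotomized IGA scores at Week 12 will be analyzed with a Cochran-Mantel-Haenszel test". No stratification variable is stated. The same section analyses lesion counts by ANCOVA with the baseline count as covariate.

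Section 7.5.1 describes the imputed IGA analysis. In each completed data set, "dichotomous endpoints (defined as IGA = 0 or 1 and at least a two-grade reduction from Baseline) will be computed". Then "Each complete data set will be analyzed with a Cochran-Mantel-Haenszel test", and "Results from these analyses will be combined into a single inference using SAS® PROC MIANALYZE". Again no stratum is stated, and the quantity to be pooled is not named.

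Inclusion criterion 3 (section 3.7.2) restricts entry to baseline IGA 3 or 4. Section 8.3 describes randomization by IWRS and states no stratification factor. Section 7.1 leaves detailed methodology to the SAP: "The SAP will be finalized before the database is locked". The SAP was not available for this review.

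**The concern.** Success is a final IGA of 0 or 1 and a fall of at least two grades. From baseline 3, grade 1 is enough, a fall of 3 - 1 = 2. From baseline 4, a two-grade fall ends at grade 2, which is not success, so at least 4 - 1 = 3 grades are needed. Baseline IGA therefore sets the height of the bar. It is likely to predict the outcome, it has only two levels, and it is recorded before randomization.

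A CMH test is built to take such a variable as a stratum. With no stratum it becomes the ordinary 2 x 2 comparison, and the baseline information goes unused. What is at stake is a little power on a co-primary endpoint with about 50 subjects in each active arm and about 50 on combined vehicle. The validity of the test is not at stake.

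**Working it through.** **Inputs from the protocol.** About 200 subjects randomized 2:2:2:1:1 (section 7.8): 200 x 2/8 = 50 per active arm and 200 x 1/8 = 25 per vehicle arm. Each active arm is compared with combined vehicle, 25 + 25 = 50, at two-sided 0.05 (section 7.1). Section 7.8 gives no response rate, effect size or power, so there is no stated figure to reproduce. All rates and severe shares below are assumptions.

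**Formula.** In stratum h, let a be the successes on active, n1 and n2 the group sizes, N = n1 + n2, and m the total successes. The expected count is E = n1 m / N and the variance is V = n1 n2 m (N - m) / [N^2 (N - 1)]. The statistic is (sum of a - E)^2 / (sum of V), referred to chi-square on 1 df. Without strata the sums have one term. With baseline IGA they have two.

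**Effect of stratifying, complete data.** Simulation of 200,000 trials per scenario, 50 v 50, vehicle v active success:
- IGA 3: 12 v 35%, 20 v 42%, 25 v 50%.
- IGA 4: 3 v 12%, 0 v 5%, 8 v 25%.
- Severe share: 10%, 25%, 40%, giving 27 scenarios.

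| Severe share | Power change, points | Median |
|---|---|---|
| 10% | -0.2 to +2.2 | +0.6 |
| 25% | -0.1 to +4.9 | +1.9 |
| 40% | +0.1 to +7.2 | +3.1 |

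The overall median is +1.5, and 3 of 27 scenarios are slightly negative. Repeat runs moved the ends by about 0.2 points. The negatives occur where the severe stratum responds at 8 v 25%, so that baseline grade separates subjects least. The +7.2 is the opposite corner: 40% severe, 0 v 5% in severe and 25 v 50% in moderate subjects. Under the null, rejection was 4.7% to 5.0% stratified and 4.6% to 5.0% unstratified.

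A second set assumed 12 v 30% (IGA 3) and 3 v 10% (IGA 4):

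| Severe share | Unstratified | Stratified |
|---|---|---|
| 5% | 59.3% | 59.5% |
| 10% | 57.7% | 58.2% |
| 20% | 54.1% | 55.3% |
| 30% | 50.8% | 52.4% |

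**Imputed version.** This followed the protocol's imputation steps with 6,000 trials per row, success about 20% v 40%, 25% severe, and a pooled risk difference. Power without and with strata was 55.6% and 58.0% at 10% missing, 53.6% and 55.6% at 15%, and 48.9% and 50.6% at 25%. The gains are 2.4, 2.0 and 1.7 points, with a Monte Carlo error of about 0.6 points on each power.

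**The clarification.** PROC MIANALYZE pools an estimate and its standard error, whereas a CMH test returns a chi-square and a p-value. Take 19/50 v 10/50 as an example:
- Risk difference: 0.18 / sqrt(0.38 x 0.62/50 + 0.20 x 0.80/50) = 0.18 / 0.0889 = 2.02, p = 0.043.
- Log odds ratio: ln[(19 x 40)/(10 x 31)] / sqrt(1/19 + 1/31 + 1/10 + 1/40) = 0.897 / 0.458 = 1.96, p = 0.0503.
- CMH: E = 14.5, V = 50 x 50 x 29 x 71 / (100^2 x 99) = 5.20, (19 - 14.5)^2 / 5.20 = 3.89, p = 0.048.

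By exact enumeration at 50 v 50, with vehicle rates of 10% to 30% and a 20-point gain, the first two disagree in 0.4% to 4.5% of trials. At null rates of 10%, 20% and 30%, the complete-data type I error is 5.9%, 5.8% and 5.5% for the unpooled-SE risk difference, 2.6%, 4.3% and 4.5% for the log odds ratio, and 4.8% to 5.0% for CMH.

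**The case against.** The strongest reply is that nothing here is wrong. The unstratified CMH test is valid, no stratified randomization is stated that the analysis would have to mirror, and the SAP may already name strata. All of that stands. It is also true that the gain cannot be known in advance. No severe share is given, and at a 5% share the severe stratum held no successes, hence no information, in 42% to 86% of simulated trials. In that case the test falls back on the moderate subjects and costs almost nothing. A small or absent gain does not argue against using a baseline value that is already collected.

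Two stronger readings are tempting. A reader might infer that the primary IGA test is invalid without strata. The simulated type I error contradicts that. A reader might also infer from section 7.5.1 that the imputed analysis uses a wrong method, because a test statistic is sent to a procedure that pools estimates. The protocol leaves one quantity unnamed and chooses no wrong one. A Mantel-Haenszel estimate is the natural companion, and a Wilson-Hilferty transformation of the CMH statistic is another route. Section 7.1 assigns such detail to the SAP. The matter touches one sensitivity analysis and leaves the LOCF-based primary result unchanged, so it is a point to confirm and not a defect.

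**Conclusion.** A minor, no-cost improvement. The protocol states no stratum for a co-primary binary endpoint whose success threshold depends on a two-level baseline grade, while its continuous co-primary endpoints are adjusted for baseline. Stratifying would typically add 1 to 2 points of power. The range is about -0.2 to +7 points, the top of which needs many severe subjects who rarely respond. Control of type I error is unaffected. These sizes rest on assumed response rates and a 10% to 40% severe share. The direction depends only on baseline IGA predicting success, which the definition of success makes plausible.

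**What to change.** Unless the SAP already names strata, state that the Week 12 IGA CMH test in section 7.5 and its imputed version in section 7.5.1 are both stratified by baseline IGA (3 v 4), specified before unblinding. Change both together, so that the sensitivity analysis differs from the primary one only in how missing data are handled.

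For clarification, confirm in the SAP which estimate and standard error, or which transformed CMH statistic, is pooled. If a risk difference with unpooled standard error is chosen, note its complete-data type I error of about 5.5% to 5.9%. In the same edit, the phrase "where nmiss is the maximum number of missing values of both treatment groups" should refer to all five treatment groups, which is a wording slip only.

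The cost is one or two sentences and a few program lines, with no new data and no change to conduct or sample size.
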